Protocol Number: 20220254

National Clinical Trial (NCT) Identified Number: NCT06938230

Principal Investigators: [name], DO & [name]

Grant Title: Maximizing Child Health and Learning Potential: How to Promote A School Culture of Safety in the era of COVID-19

Grant Number: 1OT2HD108111-01

Funded by: National Institutes of Health (NIH) - Eunice Kennedy Shriver National Institute of Child Health and Human Development (NICHD)

Version Date: April 24, 2025

1) Protocol Title

Promoting A School Culture of Safety in the era of COVID-19: Assessing Feasibility and Impact of a Health Education Initiative

2) Objectives*

The primary purpose of this study is to evaluate the feasibility and impact of a COVID-19 health initiative in at-risk urban school settings. This protocol is comprised of 3 components:

- **Part 1A:** Evaluating the feasibility and acceptability of a health education initiative in school health settings.
- **Part 1B:** Assessing COVID-19 knowledge and experience among caregivers of students in at-risk urban school settings post-intervention.
- **Part 1C:** Evaluating the impact of the health education initiative on vaccination rates and other health behaviors 3 months following the intervention.

The second purpose of this study is to compare COVID-19 knowledge, experiences, and health behaviors between participants who received the health initiative and those who did not (controls), through:

- **Part 2A:** Comparing COVID-19 knowledge, experience, and health behaviors of participants in the health education initiative to controls, immediately following the initiative.
- **Part 2B:** Comparing COVID-19 knowledge, experience, and health behaviors of participants in the health education initiative to controls, three months after the initiative.

3) Background*

Covid-19 has infected over 31 million individuals in the United States (CDC, 2021), over 3.54 million of whom were children (AAP, 2021). The pandemic has disproportionately affected racial/ethnic minorities, including children, in terms of infections, hospitalizations, and death (Lopez, Hart, & Katz, 2021; Van Dyke et al., 2021). Other sociodemographic risk factors such as household composition, socioeconomic status, limited English proficiency, housing type, and transportation are also associated with Covid-19 incidence and mortality (Karmakar, Lantz, & Tipireni, 2021).

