Participants will receive the health education session for up to 6 months.	Participants will receive a one time 45 minute intervention session. During the session participants will receive information regarding COVID-19 disease process and behavioral effects and had the opportunity to ask questions.
No Intervention: Control Group Participants in this group will not receive any health education and total participation is up to 6 months.	

Intervention Participants

Part 1A (Intervention participants only)

Overview: A health education initiative will be conducted one or more times at each intervention school (i.e., Arch Creek Elementary, Sabal Palm Elementary, JFK Middle, North Miami High, and Booker T. Washington High). This initiative will consist of a panel of health experts, individuals with firsthand experience, and other trusted messengers (e.g., teachers, student champions) presenting on the topic of COVID-19, health safety behaviors, and vaccination. Audience participation and questions will be solicited; content will be adjusted slightly to address each audience's priorities. The initiative may be recorded and made available to the broader school community to expand accessibility. The team will work with representatives from each school to determine the best method for distributing the initiative (e.g., social media). The recording will feature only the images of the panel, to protect the identity of participants.

Consent: To reduce undue burden on participants, we are requesting a waiver of written consent for this portion of the study (see the *Consent Process* section below for more details). Prior to beginning the health education initiative, participants will be provided with information about the study, including study procedures, potential risks/benefits of participation, voluntariness of the study, their right to withdraw, and contact information for the research team, and asked to complete a brief evaluation about the program. Participants will indicate their consent by completing the evaluation form.

Primary Outcome Measures: Participants can choose to complete the following measure immediately following the intervention:

- **Evaluation of acceptability of intervention as measured by Acceptability Questionnaire:**

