Part 1C: Evaluating the impact of the health education initiative on vaccination rates and other health behaviors 3 months following the intervention. Three month post surveys will be summarized and described by school. Assessing COVID-19 knowledge and experience among caregivers of students in at-risk urban school settings 3 months post-intervention.

Part 2A & 2B: Mixed models will be used to examine change in knowledge over time (repeated measure) among participants who have participated in the education session, compared to those who haven't. Likewise, vaccine confidence will be analyzed with a mixed

model to examine change over time, compared to those who did not participate in the education session.

8) Risks to Subjects*

The potential risks in this study are minimal. It is possible some subjects may experience discomfort while responding to questions about COVID-19. However, we incorporated stakeholder feedback on most acceptable methods (i.e., culturally sensitive, addressing their concerns) to discuss COVID-19 testing, diagnosis, and vaccination with participants, to minimize discomfort.

9) Potential Benefits to Subjects*

Participants may gain knowledge about how to maintain health and safety during the era of COVID-19. However, some participants may experience no direct benefit.

10) Vulnerable Populations*

N/A

11) Setting

This study will take place at 9 Miami Dade County Public Schools served by the UM School Health Initiative:

- Intervention schools: Arch Creek Elementary, Sabal Palm Elementary, JFK Middle, North Miami High, and Booker T. Washington High.
- Control schools: Fulford Elementary, Greynolds Park Elementary, North Miami Middle school, and North Miami Beach High or those who did not participate in the intervention at “intervention schools”: Arch Creek Elementary, Sabal Palm Elementary, JFK Middle, North Miami High, and Booker T. Washington High.

12) Resources Available

Our research staff consists of personnel familiar with the protocol. Members of the research team have experience in patient outreach and follow up, conduct of clinical research, statistical analysis and methodology. Additionally, students could seek comprehensive medical services delivered by the School Health Initiative.

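### Section 7 answers the three-month impact objective (Part 1C) with an attendee-only summary and names no control comparison for the health behaviors promised in Parts 2A and 2B

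*Protocol*

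**What the plan says.** **Objectives (protocol Section 2).** Part 1C is "Evaluating the impact of the health education initiative on vaccination rates and other health behaviors 3 months following the intervention". Part 2A is "Comparing COVID-19 knowledge, experience, and health behaviors of participants in the health education initiative to controls, immediately following the initiative", and Part 2B is "Comparing COVID-19 knowledge, experience, and health behaviors of participants in the health education initiative to controls, three months after the initiative". Section 3 adds a prediction that children's vaccination rates will rise.

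**Outcomes (Section 5).** Caregiver vaccination, child vaccination and the Health Behavior Questionnaire score stand under a primary heading in Part 1C for attendees and in Parts 2A and 2B for controls. They are also listed under the primary heading of Part 1A.

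**Analysis (Section 7).** For Part 1C: "Three month post surveys will be summarized and described by school". For Parts 2A and 2B: "Mixed models will be used to examine change in knowledge over time (repeated measure) among participants who have participated in the education session", with people who did not attend as the comparison, followed by "Likewise, vaccine confidence will be analyzed with a mixed" model of the same kind. No other between-group analysis is named.

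**The concern.** Section 7 goes through the study Part by Part and attaches an analysis to most of them, so it can be checked against the objectives. Two things do not fit.

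First, 1C is worded as an evaluation of impact, but its stated analysis describes attendees alone, after the session, school by school. Such a figure mixes any effect of the session with whatever vaccination and behavior these families would have shown anyway. A reader of the results could take a high percentage among attendees for an effect.

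Second, health behaviors are one of the three domains that 2A and 2B say will be compared with controls, yet neither named model addresses them. Controls are asked about vaccination and health behaviors twice, and Section 7 states no use for those answers.

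**Working it through.** The plan gives no figure to reproduce here. The check is a cross-reading of Sections 2, 5, 7 and 15.

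**Step 1. Outcomes against promises and named analyses.**

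| Outcome | Part 1C (attendees, 3 months) | Part 2B (controls, 3 months) | Control comparison promised in 2A/2B | Control model named in Section 7 |
|---|---|---|---|---|
| Health Behavior Questionnaire | primary | primary | yes, both time points | no |
| Caregiver vaccination | primary | primary | not named | no |
| Child vaccination | primary | primary | not named (rise predicted in Section 3) | no |
| Knowledge | optional battery | primary | yes, both time points | yes |
| Vaccine confidence | optional battery | primary, within the battery | not by name; part of the same battery | yes |

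**Step 2. Count.** Health-behavior comparisons promised: 2 (immediate in 2A, three months in 2B). Named in Section 7: 0. Coverage: 0 of 2. Control models named in all: 2 (knowledge, vaccine confidence).

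**Step 3. What the 1C analysis can identify.** Let p be the proportion of attendees vaccinated at three months, b the proportion that would have been vaccinated without the session, and d the effect. Then p = b + d, so d = p − b. The by-school summary estimates p only. Nothing in the attendee data estimates b, and no intervention-group survey before the session is described. Any d consistent with a plausible b fits the same p. The same holds for the mean questionnaire score. A change within attendees between the post-session form and three months would not solve this, because background change over those months would still be included.

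**Step 4. Is a comparator available?** At three months, yes. Section 5 lists the same three outcomes for attendees (1C) and controls (2B), so 2B can supply a stand-in for b, subject to confounding.

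**Step 5. Is one available immediately after the session?** The protocol is not consistent. Section 5, Part 1A introduces its list with "Primary Outcome Measures: Participants can choose to complete the following measure immediately following the intervention" and then lists vaccination and health behaviors among several outcomes. Section 15, Part 1A says that nothing is collected there except the Acceptability and Feasibility Assessment, and that this form may be anonymous. If Section 15 is right, Part 1A holds no vaccination or health-behavior data to set against 2A.

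**The case against.** The best defence is that Section 7 is a short data-management section. Its two sentences on 2A and 2B do not say that no other outcome will be compared, and an SAP may supply the rest. Experience is also promised in 2A and 2B and is touched only through vaccine confidence, which suggests that the two models may be examples. This stands as far as it goes: one cannot say that the protocol rules out a health-behavior comparison. It does not rescue 1C, where Section 7 does state an analysis and that analysis cannot meet the objective.

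Three stronger readings are tempting, and the document supports none of them.

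- A reader might infer that all three outcomes headed primary in both groups were promised a control comparison and none received one. Objectives 2A and 2B name health behaviors but not vaccination. Vaccination belongs to 1C, which sits under the first purpose, without controls. A primary heading in both groups does not by itself promise a between-group test.
- A reader might infer that raw counts will be compared, because the unit given is a number of caregivers or children. No section says so, and the objectives and the prediction speak of rates.
- A reader might infer that both time points can be repaired by adding sentences. The conflict between Sections 5 and 15 over Part 1A leaves that open for the immediate one.

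**Conclusion.** The point holds in two parts.

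- **Part 1C.** The stated analysis has no comparator and cannot support a conclusion about impact on vaccination or health behaviors. This is the firmer part, because it concerns what Section 7 states.
- **Parts 2A and 2B.** A health-behavior comparison with controls is promised at two time points and named at none. This is a mismatch between objectives and analysis text, not proof that the comparison will be left out. For vaccination the case is weaker: it rests on 1C, on the primary headings in 1C and 2B, and on the Section 3 prediction.

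No bias in percentage points is claimed, since the document gives no vaccination rates or group sizes. The conclusion assumes that the 1C summary covers attendees only, as its place under the intervention group implies. It also assumes that the attached forms, which are not reproduced, collect the outcomes as Section 5 lists them.

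**What to change.** In Section 7, under Part 2A & 2B:

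1. Name a three-month comparison of Part 1C with Part 2B for the Health Behavior Questionnaire score and for caregiver and child vaccination. Express vaccination as proportions. Account for school and adjust for the demographics already collected, leaving the choice of model to the SAP.
2. State that the result is an observational association. Randomisation is not described, and Section 5, Part 2A allows controls to be non-attenders at intervention schools.
3. Label the 1C by-school summary descriptive, with no impact conclusion drawn from it.
4. Reconcile Section 5, Part 1A with Section 15, Part 1A before adding an immediate health-behavior comparison of 1A with 2A. If vaccination status proves to be recorded in 1A, read it as a starting level: "Participants will receive a one time 45 minute intervention session", and status recorded straight afterwards can hardly reflect it.

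If the sponsor does not want these comparisons, the alternative is to reword objective 1C as descriptive and remove health behaviors from 2A and 2B.

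The cost is a few sentences, a little more analysis and a more modest conclusion. The three-month comparison needs no new survey wave. Item wording may need aligning, because Section 5 describes the 1C questions as being about the session, which controls did not attend.

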Measures: Participants will also be asked to complete the following measure immediately following the intervention:

COVID-19 Knowledge and Experience. COVID-19 knowledge and experience using items from the RADxUP common data elements and the PhenX Toolkit (Hamilton et al., 2011). Data to be collected include basic demographic data, COVID-19 knowledge and attitudes, health risk beliefs, vaccine confidence, COVID-19 related stigma/discrimination, COVID-19 trauma, and COVID-19 anxiety. Measures are attached.

Specific Secondary Outcome Measures:

- **PTSD as measured by the University of California Los Angeles (UCLA Brief COVID-19 Screen for Child/Adolescent Post Traumatic Stress Disorder (PTSD)**

- scores range from 0 to 4, higher scores indicate more symptoms of PTSD
- Time Frame: up to 6 months

- **COVID anxiety as measured by the Coronavirus Anxiety Scale**

- scores range from 0 to 4, higher scores indicate more symptoms of COVID specific anxiety
- Time Frame: up to 6 months

Part 1C

Overview: To assess the impact of the health education initiative on vaccination status and other health behaviors.

Consent: We are requesting a waiver of consent for the first section of Part C which is a few simple questions about the intervention. Informed consent will be obtained electronically via REDCap (detailed below), on paper, or verbally over the phone or in-person, with a study staff member reading aloud questions and recording the participant's responses. During the consent process, participants will be given ample time to review study procedures and provided contact information for the research team should they have questions.

Primary Outcome Measures: Participants will be asked to complete a few questions about the impact of the education session in the last 3 months. Measure is attached.

- **Number of caregivers who received COVID-19 vaccine**
 - unit of measure number of caregivers
 - Time Frame: up to 6 months
- **Number of children who received COVID-19 vaccine**
 - unit of measure number of children
 - Time Frame: up to 6 months
- **Health behaviors as measured by Health Behavior Questionnaire**
 - Scores range from 1 ("strongly disagree") to 5 ("strongly agree"), with higher scores indicating greater intent to engage in health behaviors to prevent COVID-19.
 - Time Frame: up to 6 months

If participants agree they will also be given the opportunity to complete the COVID-19 assessment battery offered in Part B for additional compensation:

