COVID-19 Knowledge and Experience. COVID-19 knowledge and experience using items from the RADxUP common data elements and the PhenX Tookit (Hamilton et al., 2011). Data to be collected include basic demographic data, COVID-19 knowledge and attitudes, health risk beliefs, vaccine confidence, COVID-19 related stigma/discrimination, COVID-19 trauma, and COVID-19 anxiety. Measures are attached.

Specific Secondary Outcome Measures:

- **PTSD as measured by the University of California Los Angeles (UCLA) Brief COVID-19 Screen for Child/Adolescent Post Traumatic Stress Disorder (PTSD)**

- scores range from 0 to 4, higher scores indicate more symptoms of PTSD
- Time Frame: up to 6 months
- **COVID anxiety as measured by the Coronavirus Anxiety Scale**
 - scores range from 0 to 4, higher scores indicate more symptoms of COVID specific anxiety
 - Time Frame: up to 6 months

Control Participants

Part 2A

Overview: Control participants will be invited to complete a survey that assesses their COVID-19 knowledge and experience. The survey will be conducted through a secure online data collection method (e.g., REDCap or Qualtrics), paper, or verbally over the phone or in-person, with a study staff member reading aloud questions and recording the participant's responses. If interested and eligible, participants will be given access to the online survey via a link sent by email or by scanning a QR code. If preferred, they will be given the option to complete the survey verbally over the phone or in-person, or to complete it on paper. Control participants may be recruited from any of the study schools (i.e., intervention or control). They must not have participated in the intervention.

Informed Consent: Informed consent will be obtained electronically via REDCap (detailed below) or via paper forms. During the consent process, participants will be given ample time to review study procedures and provided contact information for the research team should they have questions.

Primary Outcome Measures: Participants will complete the following measures:

- **Number of caregivers who received COVID-19 vaccine**
 - unit of measure number of caregivers
 - Time Frame: up to 6 months
- **Number of children who received COVID-19 vaccine**
 - unit of measure number of children
 - Time Frame: up to 6 months
- **Health behaviors as measured by Health Behavior Questionnaire**

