Co-Investigator [name] is a Professor of Public Health Sciences and the Director of Public Health Education in the Department of Public Health Sciences at the University of Miami, Miller School of Medicine. She has over 21 years of experience in the design and implementation of multisite clinical trials, and in the efficient management and oversight of remote sites and demonstrated experience in the development and implementation of trials for Hispanics and Spanish speakers. [name] research career has been committed to improving practice through the implementation of clinical trials in real-world settings, and more recently in creating the local capacities that would allow the implementation of such trials. She will be responsible for monitoring the measurement and assessment protocols and will assist in manuscript preparation. She will work closely with our statistician to prepare routine reports on data collection and analyses.

13) Prior Approvals

Approval must also be obtained by the Miami Dade County Public Schools IRB prior to commencing this study.

14) Recruitment Methods

Intervention Participants

Part 1A

Recruitment: Participants will be recruited from the following schools: Arch Creek Elementary, Sabal Palm Elementary, JFK Middle, North Miami High, and Booker T. Washington High. Parents/guardians from each school will be recruited via flyers posted at their schools (see flyer attached), sent home via mailings, or posted on school websites; advertising at school events; word of mouth by school champions; and/or school messaging systems. Additionally, individuals who indicated interest in research on clinical consent forms may be contacted. The recruitment method will depend on acceptability to administrators and the school community.

Compensation: Participants will receive \$50 payment for attending the education session and completing the feedback forms.

Part 1B

Recruitment: Immediately following the health education initiative, participants will be invited to complete additional questionnaires. They will receive a flyer with information about questionnaires (see flyer attached) and links to complete them electronically, or will be given the opportunity to complete paper forms in-person at study sites.

Compensation: Participants will receive \$20 payment for completing the post-intervention measures.

Part 1C

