Recruitment: Participants will be re-contacted via the information they provided during Part A and ask if they are still interested in participating. If so, they will be given the link to complete the consent and 3-month follow-up measures, or will be given the opportunity to complete paper forms in-person at study sites.

Compensation: Participants will receive \$30 payment for completing one measure and a \$25 payment for completing the rest of the 3-month post intervention measures if they choose to do so.

Control Participants

Part 2A

Recruitment: Participants will be recruited from the following schools: Fulford Elementary, Greynolds Park Elementary, North Miami Middle school, and North Miami Beach High; they may also be from “intervention schools,” (i.e., Arch Creek Elementary, Sabal Palm Elementary, JFK Middle, North Miami High, and Booker T. Washington High) but must not have participated in the intervention. Parents/guardians from each school will be recruited via flyers posted at their schools (see flyer attached), sent home via mailings, or posted on school websites; advertising at school events; word of mouth by school champions; and/or school messaging systems. Additionally, individuals who indicated interest in research on clinical consent forms may be contacted. The recruitment method will depend on acceptability to administrators and the school community.

Compensation: Participants will receive a \$50 payment for completing the questionnaires.

Part 2B

Recruitment:

Participants will be re-contacted via the information they provided during Part 2A and asked if they are still interested in participating. If so, they will be given the link to complete the consent and 3-month follow-up measures, or will be given the opportunity to complete paper forms in-person at study sites.

Compensation: Participants will receive a \$55 payment for completing the follow-up questionnaires.

15) Confidentiality

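### Section 7 models change between two post-session surveys, whereas Objectives 2A and 2B ask for attender-control level differences; the change contrast loses a lasting gain, and the level contrast carries self-selection in full

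*Protocol*

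**What the plan says.** Section 2 (Objectives) states Part 2A as "Comparing COVID-19 knowledge, experience, and health behaviors of participants in the health education initiative to controls, immediately following the initiative" and Part 2B as "Comparing COVID-19 knowledge, experience, and health behaviors of participants in the health education initiative to controls, three months after the initiative". Both are differences between two groups at a given time.

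Section 7 (Data Management) gives one analysis for Parts 2A and 2B together: "Mixed models will be used to examine change in knowledge over time (repeated measure) among participants who have participated in the education session", compared with people who have not. A second sentence applies the same approach to vaccine confidence. The terms named are attendance and time.

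On timing, Section 5 (Procedures Involved), Part 1B, introduces the knowledge and experience battery for attenders with "Participants will also be asked to complete the following measure immediately following the intervention". Part 1C offers the battery again at three months. No measurement before the session is described. Controls answer a first survey (Part 2A) and a second about three months later (Part 2B).

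On how people enter each group, Section 14 (Recruitment Methods) recruits parents to the session through flyers, school events, messaging and word of mouth. The battery that yields knowledge and vaccine confidence is then a further step: "Immediately following the health education initiative, participants will be invited to complete additional questionnaires". At three months it is optional again, with a separate "payment for completing the rest of the 3-month post intervention measures if they choose to do so". For controls the same items are part of the main survey. Controls are defined by not having taken part, and they may come from any of the nine schools.

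**The concern.** The stated objective and the stated analysis are different quantities, and neither isolates the effect of the session.

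The change contrast removes stable differences between the two kinds of parent, but its starting point already includes whatever the session achieved. If knowledge rises at the session and stays up, attenders show no change relative to controls, and the model reports nothing. The level contrast retains the rise, but without a pre-session value nothing absorbs what attenders already knew or believed when they decided to come.

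Section 3 predicts increased knowledge, and Section 2 speaks of impact. Followed as written, Section 7 could report a near-zero change as the answer to Objectives 2A and 2B. Alternatively, an unadjusted level difference could be read off the model and described as the session's impact.

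**Working it through.** **What each contrast estimates.** Let d be the stable attender-control difference that exists without the session, E0 the session effect at the first survey and E3 the effect at three months. Any time trend common to both groups cancels.

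- Level contrast, first survey (Part 2A): d + E0
- Level contrast, three months (Part 2B): d + E3
- Change contrast (Section 7): (d + E3) − (d + E0) = E3 − E0

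Two opposite situations with assumed values in SD units:

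| Situation | d | E0 | E3 | Level, first | Level, 3 months | Change |
|---|---|---|---|---|---|---|
| Selection only, no effect | 0.2 | 0 | 0 | 0.2 | 0.2 | 0 |
| Lasting effect, no selection | 0 | 0.2 | 0.2 | 0.2 | 0.2 | 0 |

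The expected results are identical, so the two surveys cannot tell these situations apart.

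**Size of the selection problem.** The protocol text available gives no sample size, SD or expected difference, so there is no figure to reproduce and every input here is an assumption. With nA attenders, nC controls and unit SD, SE = √(1/nA + 1/nC). For 100 v 80, SE = √(0.0100 + 0.0125) = 0.150. With d = 0.2 and no session effect, the standardised shift is 0.2/0.150 = 1.33, and a two-sided 5% t-test (noncentral t) rejects with probability 0.264.

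| Sizes | SE | d = 0.1 | d = 0.2 | d = 0.3 |
|---|---|---|---|---|
| 50 v 40 | 0.212 | 7.5% | 15.4% | 28.8% |
| 100 v 80 | 0.150 | 10.2% | 26.4% | 51.2% |
| 200 v 160 | 0.106 | 15.6% | 46.8% | 80.5% |

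The bias equals d whatever the sample size. A larger study only makes it more likely to reach significance.

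**Conditional check on standard errors.** This applies to the level contrast, and only if no school or session term is in the model. Take n per group, school intraclass correlation ρ, and a share f of controls from the four control schools, with respondents spread evenly within each set of schools. The true variance is ρ·f²·(1/5 + 1/4) + (1 − ρ)·(2/n), against 2/n if school is ignored. With assumed n = 100 and ρ = 0.05:

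- f = 1: 0.05 × 0.45 + 0.95 × 0.02 = 0.0415 against 0.0200. SE ratio 1.44; a nominal 5% test rejects about 17%.
- f = 0.5: 0.0056 + 0.0190 = 0.0246. Ratio 1.11; about 7.7%.
- f = 0: 0.0190. Ratio 0.975; about 4.4%, so slightly conservative.

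The break-even share is f = √((2/n)/0.45), which is about 0.30, 0.21 and 0.15 for n = 50, 100 and 200.

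Clustering by session alone, with an assumed session correlation of 0.05 and n = 100, gives a ratio of 1.21 with 5 sessions (10.7%) and 1.11 with 10 (7.7%).

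For the change contrast a constant school effect cancels. In simulation at n = 100 per group the SE ratio was 0.99 to 1.01, and it reached 1.18 only when a school-by-time variance of 0.02 was added.

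**The case against.** The protocol never claims randomisation. It defines controls openly as people who did not take part, and it makes this comparison its second purpose. Section 7 is a short summary. A mixed model with attendance, time and their interaction can yield the level differences as well as the change, and covariates and random effects are commonly left to a statistical analysis plan, which is not at hand. All of that is fair, and it limits the point.

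What it does not answer is that Section 7 names a quantity, change over time, and that quantity is not what Objectives 2A and 2B ask for. Nor can later covariates supply the missing pre-session value. They may reduce the bias but cannot be relied on to remove it.

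A reader might go further and infer that the plan's standard errors are too small. The documents do not support this. Section 7 does not exclude a school or session term. A constant school effect cancels from the contrast it names. For the level contrast the direction depends on the mix of controls, which the protocol leaves open: "Control participants may be recruited from any of the study schools (i.e., intervention or control". With few controls from control schools and no clustering by session, the naive standard error is slightly too large. This stays a conditional note.

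Nor do the documents show that attenders and controls do differ, or by how much. The percentages show only what a difference of a given size would do.

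**Conclusion.** The point holds. Section 7's only between-arm analysis estimates E3 − E0, which is zero for any gain that lasts, so it does not deliver the comparison in Objectives 2A and 2B. The level contrast that would deliver it takes in any stable difference between parents who attend and opt in and parents who do not attend. This follows from the protocol's own timing and recruitment and needs no assumed number.

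The size is illustrative. Under no session effect, a 0.2 SD difference gives a significant result in about 26% of studies at 100 v 80. Across the assumed sizes and differences of 0.1 to 0.3 SD, the range is about 8% to 80%. The standard-error issue is secondary and arises only under the conditions given above.

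**What to change.** In Section 7:

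- State that the Part 2A and 2B comparison is the attender-control difference in level at each survey, estimated from the mixed model and adjusted for the demographic data collected in both arms.
- State that the change contrast describes only persistence between two post-session surveys.
- Report the level difference as a non-randomised association, not as the session's causal impact.

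This takes two or three sentences and minor extra analysis, with no new data collection. It does not remove unmeasured self-selection. If adjustment removed half of a 0.2 SD difference (an assumption; the demographic items are not shown), false significance at 100 v 80 would fall from about 26% to about 10%, not to 5%.

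Conditional note: if a sizeable share of controls comes from the control schools, or outcomes cluster by session, a school-level term or school-clustered inference with small-sample degrees of freedom covers the level contrast. Sessions lie within schools, so one such term is enough. The price is wider intervals with only nine schools: in simulations of a school-level jackknife at 100 v 80, the 95% half-width rose from about 0.30 SD to between 0.36 and 0.51 SD. It widened to about 0.38 to 0.39 SD even where all controls came from the intervention schools and no correction was needed.
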